## Instructions for using this protocol template:

- Use this template for studies that involve the use of a test article (drugs or devices, supplements, alternative medicines and/or chemicals) and falls under the FDA regulations.
- Add this completed protocol template to your study in CATS IRB (http://irb.psu.edu) in the "Basic Information" section. Links to Penn State's protocol templates are available in the same location where they are uploaded and their use is required.
- This template is provided to help investigators prepare a protocol that includes the necessary information needed by the IRB to assess risks to human subjects in research.
- There may be sections in this template that do not apply. If so, provide the response "Not Applicable".
- All guidance language appears in *red italics* and should be deleted from the final version of the protocol.

## 1.0 Objectives

## 1.1 Study Objectives

This study will determine whether the negative effects of combined *oral* contraceptive (COC) therapy on bone turnover are dependent on the route of administration such that an attenuation of these effects is observed when a comparable dose of *non-oral* transdermal contraceptive (TDC) therapy and contraceptive vaginal ring (-CVR) therapy are also tested. Millions of women use COC therapy for birth control purposes or regulation of menstrual cycles. TDC and CVR therapies are relatively new FDA-approved contraceptive alternatives to COC. The purpose of the proposed project is to address the potential mechanism(s) by which *oral* ethinyl estradiol (EE) may negatively impair bone via "first pass" effects on the liver and compare these effects to *transdermally*-administered and *vaginally*-administered EE in young women. We will assess mechanistic effects by way of 2-day serial sampling and by an insulin-like growth factor (IGF-1) generation test. The IGF-1 generation test was developed over 20 years ago and is currently used to diagnose growth hormone (GH) insensitivity (Balhara et al., 2012; Buckway et al., 2001). IGF-1 generation tests may also be used to amplify effects not observable by the assessment of fasting or serial concentrations of systemic IGF-1(secreted by the liver) and its associated binding proteins (Balhara et al., 2012; Buckway et al., 2001). This study will be the first study to examine the physiological mechanisms whereby the route of estrogen administration affects the GH/IGF-1 axis and bone turnover in young women.

The **overall purpose** of this study is to explore differences in liver metabolism and bone turnover of oral versus transdermal and vaginal contraceptive therapy. In an effort to expose the route-dependent effects of oral versus transdermal and vaginal contraceptive therapy on liver and bone metabolism, we will examine the effects of ethinyl estradiol on serially-assessed fasting concentrations of the GH/IGF-1 axis and bone turnover and explore physiological mechanisms underlying hepatic responsiveness to oral versus transdermal and vaginal contraceptive therapy using an IGF-1 Generation Test as a probe.

## Specific Aim 1: To examine the effects of oral, transdermal, and vaginal contraceptive therapy on serially-assessed fasting concentrations of the GH/IGF-1 axis.

**Hypothesis 1A:** Significant declines in IGF-1 concentrations will be observed following COC therapy; whereas, TDC and CVR therapy will result in less severe declines or no change in IGF-1 concentrations, similar to Control. **Hypothesis 1B:** The most unfavorable alterations in the IGF-1 binding proteins (IGFBP-3, IGFBP-1) and the acid labile subunit (ALS) concentrations will be observed following COC therapy compared to TDC and CVR therapy and compared to Control.

Specific Aim 2: To examine the physiological mechanisms underlying the hepatic responsiveness to oral, transdermal, and vaginal contraceptive therapy by assessing the effect of exogenous GH on the GH/IGF-1 axis using an IGF-1 Generation Test.

**Hypothesis 2A:** GH-stimulated IGF-1 concentrations will be reduced to a greater extent following COC therapy compared to TDC and CVR therapy and compared to Control.

**Hypothesis 2B:** GH-stimulated alterations in IGFBP1 and IGFBP3 will be less favorable following COC therapy compared to TDC and CVR therapy and compared to Control.

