## 1.2 Primary Study Endpoints

- 1) Serially-sampled fasting serum concentrations of IGF-1, IGFBP-1, IGFBP-3, and ALS before and after contraceptive therapy
- 2) Serially-sampled fasting serum concentrations of osteocalcin, P1NP, NTx, and CTx before and after contraceptive therapy
- 3) The response of IGF-1, IGFBP-1, IGFBP-3, and ALS to exogenously administered GH before and after contraceptive therapy.

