A second mechanism that may be contributing to the suppression of IGF-1 concentrations in women taking COC is reduced hepatic responsiveness to GH. Indeed, a novel test, i.e., the IGF-1 Generation Test, can be used to test this effect. Testing the responsiveness of the liver to exogenously administered GH has the potential to amplify subtle differences and abnormalities in the liver that are not otherwise detectable from an examination of fasting concentrations alone. The IGF-1 Generation Test has been used to assess the responsiveness and/or sensitivity of the liver to GH in various disease states such as obesity and GH-deficiency (Gleeson et al., 2005; Buckway et al., 2001) and in adults during hormone therapy (Lissett and Shalet, 2003; Lieberman et al., 1994). Lieberman et al. (1994), the first investigator to use the IGF-1 Generation Test in adults, reported that postmenopausal women on estrogen therapy demonstrated an attenuated increase in IGF-1 concentrations after GH administration compared to women not on estrogen therapy. Similarly, Lissett and Shalet (2003) used the IGF-1 Generation Test in 9 postmenopausal women treated with three different formulations of estrogen for 6 weeks followed by an 8-week washout period between each treatment phase. The estrogen formulations included oral estradiol valerate, a low dose transdermal  $E_2(50 \text{ ug/d})$  and high dose transdermal  $E_2(200 \text{ ug/d})$ . In response to GH stimulation, serum IGF-1 concentrations were significantly lower after oral estrogen treatment and high dose transdermal treatment than prior to estrogen treatment. However, with low dose transdermal E2, serum IGF-1 concentrations were no different in response to GH administration than those measured prior to treatment. All three estrogen formulations caused a reduced response of IGFBP-3 to GH stimulation; however, an attenuated response of ALS was only observed during transdermal treatment (both high and low dose). These results indicate that the suppressed IGF-1 concentrations observed in postmenopausal women on estrogen therapy may be due to reduced responsiveness of the liver to GH. In addition, these results also suggest that high doses of estrogen may influence responsiveness to GH regardless of the route of administration. The IGF-1 Generation Test, however, has never been performed in premenopausal women taking COC, TDC, and CVR and will provide valuable information about the impact of exogenous estrogens used for contraceptive purposes on the GH/IGF-1 axis and perhaps help to explain some of the negative effects of COC therapy on the skeleton.

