# 6.2.2 Baseline: After subjects complete screening, the Baseline Period will begin on the first day of their next menstrual period and continue until the first day of their next menstrual period. During this time the following procedures for Baseline will occur. The number of visits and the length of each visit will be determined by the subject's preference and schedule.

2-day Fasting Blood Sampling to Establish Fasting Concentrations of GH/IGF-1 Axis and Bone Metabolism: During days 2-7 of the baseline period, blood will be obtained on 2 consecutive days for the IGF-1-related measures of IGF-1, IGFBP-1, IGFBP-3, and ALS, and for markers of bone turnover. Subjects will report to the CRC in the fasted state (no food for 8 hours prior the appointment) in the morning on 2 consecutive days between 0700-0800 hours. Subjects will remain in supine position for 15 minutes prior to the collection of each blood sample.

IGF-1 Generation Test: To assess the impact of COC/TDC/CVR therapy on responsiveness to GH, the IGF-1 Generation Test will be conducted during the first two weeks of baseline.

On the second day of the 2-day fasting blood samples, study participants will be injected subcutaneously with recombinant human GH (rhGH) (Omnitrope) in the morning by a nurse at the CRC at a dose of 0.033 mg/kg/d subcutaneously (Coutant et al., 2012). This dose has previously been used in adults without side effects and is comparable to that administered in the laboratory of our co-investigator, [name] (Fazeli, et al., 2010b). These injections will occur each morning for the following 3 days. A urinary pregnancy test will be performed prior to initiation of GH administration.

On day 2, day 4, and day 6 *after* subcutaneous administration of GH begins, study participants will again report to the CRC in the morning between 0700-0800 hours in a fasted state for a single blood draw for analysis of IGF-1, IGFBP-1, IGFBP-3, and ALS. Subjects will remain in supine position for 15 minutes prior to the collection of each blood sample.

Subjects will be asked to refrain from resistance training for the duration of the IGF-1 generation test.

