## 8.0 Statistical Plan

#### 8.1 Sample size determination

Because this is a pilot study to obtain preliminary data for submission of an NIH R01 proposal, we aim to complete 12 subjects in each of 4 groups (COC group, TDC group, CVR group, and control), totaling 48 subjects.

Power analysis is based on the primary endpoint, i.e., average change in IGF-1 levels with the IGF-1 generation test over 28 days in the groups receiving TDC vs. COC. A total of 12 participants (6 each in the COC and TDC estradiol arms) will be required to detect a difference of 1.348\*SD in mean change in IGF-1 levels in groups receiving TDC vs. COC, with a power of 86%, using a two sided p=0.05 level test (Weissberger et al., 1991). Because we are adding a group and to ensure that we see a difference among the groups, we aim to complete 12 subjects per group.

To account for a potential screening failure rate of 33% and potential drop-out rate after randomization of 30%, we plan to enroll a total of 100 subjects (25 per group).

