## 8.2 Statistical methods

To determine baseline differences among groups, we will use a one-way analysis of variance (ANOVA). For longitudinal analyses, repeated measures ANOVA as well as mixed linear models will be used to determine if response of the GH/IGF-1 axis to 1) route of administration of contraceptive therapy and 2) exogenous GH differs among groups before and after contraceptive therapy.

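### Hypothesis 2A is worded on the GH-stimulated IGF-1 level while the endpoint and analysis use an undefined response, so a fall in fasting IGF-1 alone could be misread as reduced hepatic responsiveness

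*Combined protocol and SAP*

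**What the plan says.** Specific Aim 2 (Section 1.1) addresses how responsive the liver is to GH, "by assessing the effect of exogenous GH on the GH/IGF-1 axis using an IGF-1 Generation Test". Section 2.3 gives the reason: "A second mechanism that may be contributing to the suppression of IGF-1 concentrations in women taking COC is reduced hepatic responsiveness to GH". It presents the test as able to show differences that fasting values miss.

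The quantity to be compared is described in four ways:

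- **Hypothesis 2A (Section 1.1):** "GH-stimulated IGF-1 concentrations will be reduced to a greater extent following COC therapy". This is a level.
- **Endpoint 3 (Section 1.2):** "The response of IGF-1, IGFBP-1, IGFBP-3, and ALS to exogenously administered GH before and after contraceptive therapy". This is a response, without a formula.
- **Section 8.1:** "average change in IGF-1 levels with the IGF-1 generation test over 28 days in the groups receiving TDC vs. COC". This is a change with no stated reference point, and it is called the primary endpoint for the power analysis.
- **Section 8.2:** repeated measures ANOVA and mixed linear models ask whether the response to "exogenous GH differs among groups before and after contraceptive therapy". No model terms are listed.

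Hypothesis 1A states separately that "Significant declines in IGF-1 concentrations will be observed following COC therapy", with smaller or no declines on TDC and CVR.

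At baseline (Section 6.2.2), "On the second day of the 2-day fasting blood samples, study participants will be injected subcutaneously with recombinant human GH". Blood is drawn again on days 2, 4 and 6 after GH starts.

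**The concern.** The generation test is there to separate two explanations of low IGF-1 on COC: less GH reaching the liver, or a liver that responds less to GH. A stimulated concentration does not separate them, because it carries the starting value with it. If fasting IGF-1 falls on COC, as Hypothesis 1A expects, and each woman's rise after GH is unchanged, the stimulated concentration is still lower on COC. Hypothesis 2A would then be confirmed by the finding that confirms 1A, and Aim 2 would credit the liver with an effect that was not there.

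Nothing elsewhere in the plan settles the matter. No section says whether the response is a level, a peak, an increment, a ratio or an area under the curve. No section names a pre-GH reference sample, adjusts for pre-GH IGF-1, or says how days 2, 4 and 6 are combined. Section 8.1 sizes the study on the generation-test change, so the gap affects the powered outcome.

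**Working it through.** **Step 1. Decompose the level.** Let F be the pre-GH fasting value, R the GH-induced rise and S = F + R the stimulated level. Over therapy, ΔS = ΔF + ΔR. The between-arm difference in mean ΔS is therefore the difference in ΔF plus the difference in ΔR. With no difference in ΔR, it equals the fasting difference.

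**Step 2. Example with assumed values.** Fasting IGF-1 falls from 300 to 240 and the rise stays at 200.

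- Level: 500 to 440, and 440/500 − 1 = −12%.
- Increment: 200 to 200, unchanged.
- Fold rise: 500/300 = 1.67 to 440/240 = 1.83, an increase.

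The three measures give three different answers from the same data.

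**Step 3. The plan's own power figure.** Section 8.1 states 86% power for 1.348 SD with 6 per arm, two-sided 0.05. Recomputed, this is 64.6% (normal approximation) or 55.9% (noncentral t). With the planned 12 completers per arm it is 91.0% or 88.4%. The 86% is not reproduced; that is a separate matter and does not decide this point. Only two figures are carried forward: 12 per arm, and 1.348 SD as a scale. Section 8.1 attaches 1.348 SD to IGF-1 change with the generation test, so using it below for a fasting difference is an assumption.

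**Step 4. How often a level test would be significant with no difference in the rise.** Inputs:

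- n = 12 per arm (Section 8.1), two-sample t-test, two-sided 0.05.
- SD of ΔF set to 1; SD of ΔR = s, with s = 0.5 or 1.0 (assumed).
- Correlation of ΔF and ΔR = ρ, from −0.5 to +0.5 (assumed).
- Between-arm difference in mean ΔF = k SD (assumed); difference in mean ΔR = 0.

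SD(ΔS) = √(1 + s² + 2ρs). The standardised difference is d = k / SD(ΔS). The noncentrality is d√(12/2), with 22 degrees of freedom.

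| s | ρ | SD(ΔS) | k = 0.5 | k = 1.0 | k = 1.348 |
|---|---|---|---|---|---|
| 0.5 | −0.5 | 0.866 | 27% | 77% | 95% |
| 0.5 | 0 | 1.118 | 18% | 55% | 81% |
| 0.5 | +0.5 | 1.323 | 14% | 43% | 67% |
| 1.0 | −0.5 | 1.000 | 22% | 65% | 88% |
| 1.0 | 0 | 1.414 | 13% | 38% | 61% |
| 1.0 | +0.5 | 1.732 | 10% | 27% | 45% |

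A simulation at ρ = 0 (20,000 trials per setting) agrees: 13-18%, 39-56% and 61-80% for the three values of k. A test on the increment depends only on ΔR and was significant in about 5% throughout.

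**Step 5. Can the increment be computed?** At baseline, yes: the second fasting sample falls on the first injection day. Post-study, Section 6.2.4 places the two fasting samples within days 1-3 but lets the generation test begin on any of days 1-7. The last fasting sample could be on day 2 and the first injection on day 7, which is 5 days apart. Section 6.1 ties the two together only where the optional 5-hour sampling is done. Section 6.2.4 also leaves IGFBP-1 off the post-study fasting list, although Sections 1.2 and 6.1 include it.

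**Step 6. Combining the draws.** GH is given on four consecutive days, so the day 6 draw follows the last injection. An average of days 2, 4 and 6 mixes values during and after dosing.

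**The case against.** The strongest reply is that the plan does not commit to a test of the stimulated level. A reader might infer that it does from Hypothesis 2A, but 2A is one narrative sentence. The aim, endpoint 3 and Sections 8.1 and 8.2 all speak of an effect, response or change, and a repeated measures model that includes the pre-GH sample would test the rise. This stands. The defect is a level-worded hypothesis beside an undefined response.

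A reader might also infer that the stimulated level must fall whenever fasting IGF-1 falls. That holds only if the rise does not increase enough to offset the fall, and the documents do not say how the rise behaves.

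The level also has precedent. Section 2.3 describes one earlier study in terms of a smaller increase after GH and another in terms of lower stimulated concentrations, and reads the latter as reduced responsiveness. This explains the wording of 2A. It also shows that the protocol never chose between the two.

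Nor is the increment the only defensible scale. If the liver's response were proportional, the example in Step 2 would give 240 × 500/300 = 400. The increment would be 160 rather than 200 with the fold rise unchanged. That is a reason to report the fold rise as well; it does not support leaving the measure open.

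Finally, this is a pilot, and fasting IGF-1 is itself a primary endpoint, so readers would see a fasting fall beside the stimulated values. That softens the consequence but does not remove it.

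**Conclusion.** The point holds in this form: 2A is worded as a level, the response is defined nowhere, and the two can lead to opposite conclusions about the liver. With no true difference in the GH-induced rise, a level test would be significant in about 27-77% of trials at a 1.0 SD fasting difference and 45-95% at 1.348 SD, against 5% for an increment test. At 0.5 SD the range is 10-27%.

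These figures illustrate the problem and do not predict this trial. They assume 12 per arm, an SD of increment change 0.5 to 1.0 times that of the fasting change, a correlation of −0.5 to +0.5, and a simple t-test on change, which Section 8.2 does not name. If the rise is equal in both arms and fasting IGF-1 falls more on COC, the direction does not depend on the SDs or correlation.

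A reader might conclude that the trial cannot answer its mechanistic question. The documents do not support that: pre- and post-GH blood is drawn in both periods, and a rise can be analysed once it is defined. The matter should be settled before analysis.

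**What to change.** 1. Reword Hypothesis 2A, and align endpoint 3 and Sections 8.1 and 8.2, to the GH-induced change from a named pre-GH fasting sample in the same period. Hypothesis 2B already refers to alterations and needs only the same definition.
2. Test it in the planned mixed model with the pre-GH sample included, using the group by period by pre/post-GH contrast. Alternatively, compare the post-study increment between arms, adjusted for the baseline increment.
3. Name the pre-GH reference for each period. Reconcile the day 1-3 fasting window with the day 1-7 start in Section 6.2.4, and the missing post-study IGFBP-1 with Section 1.2.
4. State in advance how days 2, 4 and 6 are combined, and how day 6 is treated given that it follows the last injection.
5. Report absolute stimulated levels descriptively, and the fold rise descriptively as a sensitivity analysis.

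The cost is mainly wording, with no new visits or blood draws. If the post-study fasting list in Section 6.2.4 was followed literally, IGFBP-1 would have to be assayed in those samples. The increment carries the noise of the pre-GH value; averaging the two fasting days reduces this.

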## Specific Aim 3: To examine the effects of oral, transdermal, and vaginal contraceptive therapy on serially-assessed fasting concentrations of markers of bone turnover.

**Hypothesis 3A:** A significant *reduction* in serum markers of bone formation (osteocalcin, P1NP) will be observed following COC therapy; whereas, TDC and CVR therapy will result in less severe reductions or no change in markers of bone formation, similar to controls.

**Hypothesis 3B:** A significant *reduction* in serum markers of bone resorption (NTx and CTx) will be observed following COC therapy; whereas, TDC and CVR therapy will result in less severe reductions or no change in markers of bone resorption, similar to controls.

## 1.2 Primary Study Endpoints

- 1) Serially-sampled fasting serum concentrations of IGF-1, IGFBP-1, IGFBP-3, and ALS before and after contraceptive therapy
- 2) Serially-sampled fasting serum concentrations of osteocalcin, P1NP, NTx, and CTx before and after contraceptive therapy
- 3) The response of IGF-1, IGFBP-1, IGFBP-3, and ALS to exogenously administered GH before and after contraceptive therapy.

## 1.3 Secondary Study Endpoints

Preadipocyte factor 1 (Pref-1) and sclerostin, two proteins that have recently been observed to play a role in bone health in adolescent girls and women (Fazeli et al., 2010a; Fazeli et al., 2013), may also be assessed.

## 2.0 Background

## 2.1 Scientific Background and Gaps

Despite widespread use of combined oral contraceptive (COC) therapy, investigators to date have failed to definitively answer a basic question: Is COC therapy helpful or harmful to bone health in the 18 million premenopausal women who use them (Enewold et al., 2010). Since COC preparations are often adopted for use by millions of women, understanding the negative outcomes on bone are critically important. For physically active women, COC use may pose a unique threat since recent findings suggest that COC in combination with exercise may be particularly detrimental to bone (Weaver et al., 2001; Burr et al., 2000). The physiological mechanism for the harmful effects of COC use on bone likely involves the growth hormone (GH)/ insulin-like growth factor-1 (IGF-1) axis and suppression of IGF-1 production, and these effects may be dependent on the route of contraceptive administration (Leung et al., 2004). Transdermal contraceptive (TDC) and vaginal contraceptive (CVR) therapies may offer good alternatives to COC therapy because they may *not* suppress hepatically-driven IGF-1 anabolic effects on bone formation in healthy menstruating women. To date, there are no direct comparisons among COC, TDC, and CVR therapies that explore the influence of contraceptives on the GH-IGF-1 axis in healthy young women. The proposed study will address this major gap in the literature.

## 2.2 Previous Data

## 1) Prior work by the PI ([name]) demonstrated the negative impact of COC use on bone turnover in young women (Vescovi et al., 2008).

Premenopausal women with exercise associated menstrual disturbances (EAMD) (n=6) were assigned to receive two weeks of COC therapy (EAMD+OC) or not (EAMD Control) (n=6). COC therapy was one 28-day cycle of norgestimate (NGM) and ethinyl estradiol (EE). After two weeks, serum concentrations of a marker of bone formation, PINP, and a marker of bone resorption, sCTX, were reduced by 30-40% in EAMD+OC when compared to EAMD Controls (+14%). This finding has been reported by others (Grinspoon et al., 2003; Warren et al., 2005) in response to a randomized clinical trial (RCT) (Grinspoon et al., 2003) over a longer time frame of 10 months (Warren et al., 2005). Reductions in bone turnover could compromise bone remodeling in exercising women.

